### 6.3.1 Primary Efficacy Endpoint

Subjects are instructed to report headache occurrence, headache pain features and associated symptoms, aura occurrence, and medication (i.e., triptan, ergotamine, lasmiditan, ubrogepant, or other) used to treat headache or aura in the eDiary headache report every day in the OP and DBT Phase.

Migraine days per month are assessed as “migraine days per 4 weeks” to correspond with the 4-week visit schedule. Migraine days per month are based on 4-week intervals, and are prorated to account for missing migraine reports.

See Section 9.2.2 for the definition of eDiary efficacy data days, and Section 9.2.5 for the definition of migraine days.

The number of migraine days per month in the DBT Phase is examined relative to the number of migraine days per month in the OP for the migraine analysis set, i.e., subjects with  $\geq 14$  days of eDiary efficacy data in both the OP analysis period and  $\geq 1$  month (i.e., 4-week interval) in the on-DBT efficacy analysis period.

Months in the DBT Phase are defined as follows:

- Month 1:  $\leq 4$  weeks; study days 1 to 28
- Month 2:  $>4$  to  $\leq 8$  weeks; study days 29 to 56
- Month 3:  $>8$  to  $\leq 12$  weeks; study days 57 to 84.

Analyses are based on eDiary efficacy data dates in the OP and on-DBT efficacy analysis periods.

The number of migraine days per month is prorated to 28 days and derived as follows:

- OP:  $28 \times (\text{total number of migraine days in the OP analysis period}) / (\text{total number of eDiary efficacy data days in the OP analysis period})$ . Subjects must have  $\geq 14$  days of eDiary efficacy data (not necessarily consecutive) in the OP to be evaluable.
- Month (i.e., 4-week interval) in the on-DBT efficacy analysis period:  $28 \times (\text{total number of migraine days in the month}) / (\text{total number of eDiary efficacy data days in the month})$ .

Subjects must have  $\geq 14$  days of eDiary efficacy data (not necessarily consecutive) in the specified month to be evaluable.

- Overall DBT:  $28 \times (\text{total number of migraine days through Month 3 in the on-DBT efficacy analysis period}) / (\text{total number of eDiary efficacy data days through Month 3 in the on-DBT efficacy analysis period})$ .

#### 6.3.1.1 *Missing Efficacy Data*

The frequency table of missing efficacy data in the OP and DBT Phase is provided for the DBT efficacy analysis set, and displays the following categories:

- Included in the migraine analysis set:  $\geq 14$  days of eDiary efficacy data in both the OP and  $\geq 1$  month (i.e., 4-week interval) of the DBT Phase
  - Month 1:  $\leq 4$  weeks \*
  - Month 2:  $>4$  to  $\leq 8$  weeks \*
  - Month 3:  $>8$  to  $\leq 12$  weeks \*
- Excluded from the migraine analysis set
  - $<14$  days of eDiary efficacy data in the OP
  - $<14$  days of eDiary efficacy data in all months of the DBT Phase.

In the categories marked with “\*”, subjects must have  $\geq 14$  days of efficacy data (not necessarily consecutive) in the specified month to be evaluable.

#### 6.3.1.2 *Migraine Days per Month Changes From OP Over Time on DBT: Descriptive Analyses*

The table of values and changes (both absolute and percent) from the OP in the number of migraine days per month in the DBT Phase is provided for the migraine analysis set, and summaries parameters descriptively as continuous variables (including 2-sided normal 95% CIs for mean change) by treatment group and by headache pain intensity in each month of the DBT Phase and overall DBT. Headache pain intensity categories are (1) total (mild, moderate, severe, or not reported) and (2) moderate or severe. The table also displays results by subgroup level for all efficacy subgroups of interest described in Section 4.3.

In the percent change analyses, subjects must also have  $\geq 1$  migraine day (i.e., absolute not prorated) of appropriate pain intensity in the OP analysis period to be included.

#### 6.3.1.3 *Migraine Days per Month Changes From OP Over Time on DBT: Treatment Group Comparisons*

Analyses are based on the migraine analysis set and total pain intensity, unless otherwise specified.

### Main Analysis: Migraine Analysis Set

The main analysis of the primary endpoint uses a linear mixed effects model with repeated measures and the following attributes:

- Variables: change from the OP in number of total migraine days per month as the dependent variable; treatment group, 4-level randomization stratum, categorical month (i.e., Months 1 to 3 of the DBT Phase), and the month-by-treatment group interaction as fixed effects.
- Covariance structure for repeated measures accounting for within-subject correlated errors: assumed to be homogeneous across treatment groups, and initially specified as unstructured. If the model fails to converge or cannot be fit with an unstructured covariance structure, then other covariance structures are specified in the following hierarchical order: Toeplitz (which has heterogeneous variances and heterogeneous correlations between elements); first-order autoregressive with heterogeneous variances; and first-order autoregressive with homogeneous variances.
- SE estimation method: Huber-White “sandwich” (refer to the Core SAP).

The table displays the following model estimates:

- Least-squares mean (LSM) change from OP, SE, and 95% CI by month and overall DBT for each treatment group
- Difference in LSM changes from OP between rimegepant and placebo (rimegepant – placebo), SE, 95% CI, and p-value at each month and overall DBT. Results in the overall DBT support the primary objective, results in the first month support key secondary objective #2, results in the last month support key secondary objective #3, and results in the second month support exploratory objective #1.

See Section 9.3.1 for example SAS code.

These main analyses are repeated for moderate or severe headache pain intensity to support exploratory objective #1. All variables in the model are the same, except change from the OP in number of moderate or severe migraine days per month is the dependent variable. The corresponding table has the same format.

A line plot with error bars displays the LSM change from OP in the number of total migraine days per month on the y-axis versus month of the DBT Phase on the x-axis by rimegepant treatment group. Error bars denote 95% CIs for LSM changes.

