9.1. Sample Size

The study will randomize approximately 300 subjects per treatment group. Based on data from study BHV3000-305 and subgroup analysis from the galcanezumab Phase 3 program,^{6,9,10} we estimate that rimegepant will provide roughly a 1.0-day advantage over placebo on the primary endpoint, and assuming a common standard deviation of 3.6 days. Assuming that roughly 280 subjects per treatment group will contribute to the final migraine analysis dataset, the study will have roughly 90% power on the primary endpoint at a 2-sided alpha level of 0.05.

In study BHV3000-305, rimegepant dosed EOD provided a 1.0-day advantage over placebo dosed EOD in subjects who were not taking prophylactic migraine medication through randomization. Using the data from study BHV3000-305, the standard deviation of the primary endpoint was estimated to be roughly 3.6 days for these subjects.

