9.3.1. Efficacy Analyses

9.3.1.1. Primary Endpoint

The primary endpoint will be assessed for the DBT migraine analysis set using a linear mixed effects model with repeated measures that will include the following variables: change from the Observation Phase in the number of migraine days per month as the dependent variable; and fixed effects for treatment group, randomization stratum (i.e., 4 levels), month, and month-by-treatment group interaction. Migraine days are of any headache pain intensity. Months are defined using 4-week intervals as Month 1 (Weeks 1 to 4), Month 2 (Weeks 5 to 8), and Month 3 (Weeks 9 to 12). The number of migraine days per month is prorated to 28 days account for days with missing migraine data. The difference estimate (rimegepant – placebo), standard error (SE), p-value, and 95% confidence interval (CI) will be reported for the entire DBT Phase (Weeks 1 to 12).

The repeated measures error structure is assumed to be constant across treatment groups and will be initially specified as unstructured. If the model fails to converge or cannot be fit with an unstructured error structure, then a heterogeneous Toeplitz error structure will be attempted. If the Toeplitz fails, then an autoregressive order 1 error structure will be attempted.

The Huber-White robust “sandwich” estimator will be used for the estimation of SEs, which does not require constant response variances between treatment groups and different baseline covariate values.

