## 5 SAMPLE SIZE, POWER, AND TYPE 1 ERROR

The study randomizes approximately 300 subjects per treatment group. Based on data from study C4951025 (BHV3000-305) and subgroup analysis from the galcanezumab Phase 3 program, we estimate that rimegepant provides roughly a 1.0-day advantage over placebo on the primary endpoint, and assuming a common standard deviation (SD) of 3.6 days. Assuming that roughly 280 subjects per treatment group contribute to the final migraine analysis dataset, the study has roughly 90% power on the primary endpoint at a 2-sided alpha level of 0.05.

In study C4951025 (BHV3000-305), rimegepant dosed EOD provided a 1.0-day advantage over placebo dosed EOD in subjects who were not taking prophylactic migraine medication through randomization. Using the data from study C4951025 (BHV3000-305), the SD of the primary endpoint was estimated to be roughly 3.6 days for these subjects.

Type 1 error is controlled using a 2-sided alpha level of 0.05 and hierarchical testing. First, the significance of the primary endpoint is evaluated at the 2-sided alpha level of 0.05 for rimegepant versus placebo. If the primary endpoint is not significant (i.e.,  $p\text{-value} > 0.05$ ), then any further tests on key secondary endpoints will have p-values presented only for descriptive purposes. If the primary endpoint is significant (i.e.,  $p\text{-value} \leq 0.05$ ), then the key secondary endpoints are tested hierarchically, each at a 2-sided alpha level of 0.05, in the order specified in Section 3.2.2.1. Thus, a key secondary endpoint is tested only if the preceding key secondary endpoint in the hierarchy is determined to be significant (i.e.,  $p\text{-value} \leq 0.05$ ). If a test in the hierarchy is not significant, then any further tests on endpoints in the sequence have p-values presented only for descriptive purposes, and no conclusions are drawn from those results.

For testing of other secondary or exploratory endpoints, no attempt is made to adjust for multiplicity. These endpoints are evaluated at an unadjusted, 2-sided alpha level of 0.05, and p-values are presented only for descriptive purposes.

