### J2R Imputation Sensitivity Analysis: DBT Efficacy Analysis Set

A sensitivity analysis of the primary endpoint uses the same model as the main analysis, but with jump to reference (J2R) to impute missing data (i.e., change from OP in the number of total migraine days per month) in Months 1 to 3 for the DBT efficacy analysis set. Placebo is considered the “reference”.

The analysis is performed using the following steps:

- 1) Data are imputed under J2R using specific multiple imputation SAS macros for  $n = 30$  data sets.
  - a) Subjects with <14 days of eDiary efficacy data in a specified month in the on-DBT efficacy analysis period have missing data imputed in that month.
  - b) Data imputation is applied to rimegepant and placebo.
  - c) The imputation model uses the following variables: age, sex, race, 4-level randomization stratum, and treatment group. Race may be reduced to fewer levels (e.g., white versus non-white) based on the availability of data.
  - d) The macros are run in the following order: %part1A; %part1B using  $n = 200$  data sets (Ndraws parameter) and  $n = 100$  for Markov chain Monte Carlo (MCMC) chain thinning (thin parameter); %part2A; and %part2B. Note that the Ndraws and thin parameters may be modified as needed (e.g., to decrease Monte Carlo error and autocorrelation).
- 2) Each imputed data set in step 1 is analyzed using the same model from the main analysis (see Section 9.3.1).
- 3) Results from each model analysis in step 2 are combined to produce a pooled difference in LSM change, SE, 95% CI, and p-value using SAS proc mianalyze.

The corresponding table has the same format as the one for the main analysis.

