#### **Treatment Group Comparisons**

For each domain, analyses are based on the evaluable DBT efficacy analysis set, where evaluable subjects are defined as those with nonmissing domain scores at both baseline and  $\geq 1$  scheduled

time point (i.e., Week 4, 8, or 12) during the DBT outcomes research analysis period. Treatment groups are compared using a linear mixed effects model with the following attributes:

- Variables: change from baseline in the score as the dependent variable; baseline score as a covariate; treatment group, 4-level randomization stratum, categorical week (i.e., Weeks 4, 8, and 12 of the DBT Phase), and the week-by-treatment group interaction as fixed effects.
- Covariance structure for repeated measures accounting for within-subject correlated errors: see Section 6.3.1.3.
- SE estimation method: see Section 6.3.1.3.

The table displays the following statistics and model estimates for each domain:

- Number of evaluable subjects in each treatment group
- LSM change from baseline, SE, and 95% CI by week for each treatment group
- Difference in LSM changes from baseline between rimegepant and placebo (rimegepant – placebo), SE, 95% CI, and p-value at each week. Results for the restrictive role function domain score at Week 12 support key secondary objective #4, and results for all other domain scores or time points support other secondary objective #5.

See Section 9.3.1 for example SAS code.

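### The primary model adjusts for Observation Phase migraine frequency only through a two-level split; adding the continuous count would give a small, nearly free gain in precision

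*SAP*

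**What the plan says.** SAP 6.3.1.3 models change from the OP in total migraine days per month with "treatment group, 4-level randomization stratum, categorical month (i.e., Months 1 to 3 of the DBT Phase), and the month-by-treatment group interaction as fixed effects". Protocol 9.3.1.1 agrees: "fixed effects for treatment group, randomization stratum (i.e., 4 levels), month, and month-by-treatment group interaction". The MODEL statement in SAP 9.3.1 contains those four terms and nothing else.

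The stratum (SAP 4.3) crosses OP migraine days, <8 or ≥8, with the number of oral preventive categories with inadequate response, <3 or ≥3. Eligibility allows 4 to 14 OP migraine days.

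This one model supplies the primary contrast (overall DBT), key secondary 2 (first month) and key secondary 3 (last month).

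For the MSQ, SAP 6.5.1 specifies "change from baseline in the score as the dependent variable; baseline score as a covariate", together with the same 4-level stratum. The MIBS, MFIQ, WPAI, PGA and HIT-6 change models follow that pattern, using an imputed baseline for MFIQ and PGA. No reason is given for treating migraine days differently.

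The jump-to-reference (J2R) sensitivity analysis also has no OP count: "The imputation model uses the following variables: age, sex, race, 4-level randomization stratum, and treatment group". The tipping-point imputation model adds the monthly change scores to those variables, but not the OP count.

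**The concern.** The dependent variable is DBT days minus OP days, so it contains the OP count. Change is unrelated to OP count within a stratum only if DBT days track OP days one for one. If they persist at 0.7 to 0.5 day per OP day, the slope of change on OP count is -0.3 to -0.5. The split cannot tell a subject with 4 OP days from one with 7, or one with 8 from one with 14, so that part of the variation stays in the residual.

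At stake is the width of the confidence interval for the primary endpoint and for key secondaries 2 and 3. There is also some exposure to chance imbalance in OP days within strata. The value needed is already held for every subject in the migraine analysis set, because the change score cannot be computed without it.

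**Working it through.** **The plan's own figure.** SAP Section 5 assumes that "rimegepant provides roughly a 1.0-day advantage over placebo on the primary endpoint", "assuming a common standard deviation (SD) of 3.6 days", and about 280 analysed subjects per arm. It concludes that "the study has roughly 90% power on the primary endpoint at a 2-sided alpha level of 0.05"; Protocol 9.1 says the same.

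- SE = 3.6 × √(2/280) = 0.304
- z = 1.0/0.304 = 3.287
- Power = Φ(3.287 - 1.960) = 90.8% (noncentral t: 90.7%)
- n per arm for 90% power = 273

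The stated power reproduces.

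**What the split already captures (assumption).** The OP distribution is not given, so four shapes on 4 to 14 were tried.

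| Assumed OP distribution | Within-stratum variance | Share of OP variance captured by the split |
|---|---|---|
| Uniform | 3.00 | 70% |
| Weighted to low counts | 2.36 | 73% |
| Bell-shaped around 8.5 | 2.14 | 63% |
| Weighted to high counts | 3.25 | 66% |

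**What the continuous count adds (assumption).** The slope b of change on OP count is not given either. Take 3.6 as the SD after stratum adjustment. Then R² = b² × (within-stratum variance)/3.6², and the new SD is 3.6 × √(1 - R²). For example, with b = -0.5 and variance 3.25:

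- R² = 0.25 × 3.25/12.96 = 0.063
- SD = 3.49
- Power = 92.4%

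Across the four distributions, at 280 per arm:

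| Slope | SE reduction | Power | n per arm for 90% power |
|---|---|---|---|
| 0 | 0% | 90.8% | 273 |
| -0.3 | 0.7-1.1% | 91.2-91.4% | 267-269 |
| -0.5 | 2.1-3.2% | 91.9-92.4% | 256-262 |
| -0.7 | 4.1-6.3% | 92.9-93.9% | 239-251 |

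For slopes of -0.3 to -0.5 this equals 4 to 17 fewer subjects per arm for 90% power (273 - 269 to 273 - 256). At -0.7 it is at most 34 (273 - 239).

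**If 3.6 is instead the raw SD.** The documents do not say which it is. At slope -0.5, power is 92.6-94.2% with the stratum alone and 93.6-95.5% with the continuous count. The gain is similar, from a higher base.

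**Chance imbalance.** The SD of the between-arm difference in OP days within strata is √(2 × 2.14/280) = 0.12 to √(2 × 3.25/280) = 0.15 day. It enters the treatment difference multiplied by the slope. At -0.5, a 2-SD imbalance moves the estimate by 2 × 0.5 × 0.12 = 0.12 to 2 × 0.5 × 0.15 = 0.15 day, against an assumed effect of 1.0.

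**Months 1 and 3.** The documents give no month-specific SD, so no gain can be computed for key secondaries 2 and 3. The direction should be the same.

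**The case against.** The case for leaving the model alone is reasonable. Randomisation keeps the stratum-adjusted contrast unbiased, planned power is met, and protocol, SAP and code agree. OP frequency is already a stratification factor, whereas the questionnaire baselines are not, which may explain the different models. The size of the gain depends on a slope and a distribution that the documents do not supply, and it could be nil. All of this stands as a limit on importance. The stratification argument does not, however, recover the information lost within strata, and the questionnaire models show that the plan is content to use stratum and continuous baseline together.

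Three stronger readings should be resisted:

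- A reader might infer that the primary analysis is invalid or the trial underpowered. The reproduced 90.8% and the randomised design do not support that.
- A reader might infer that <8 versus ≥8 days is the only baseline information in the model. The stratum also carries the number of preventive categories.
- A reader might infer that any within-stratum imbalance passes in full into the treatment difference. It passes only in proportion to the slope, and OP values are tabulated by arm (SAP 6.2.5.2).

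One practical objection also stands. J2R and tipping-point use the DBT efficacy set, which has no OP diary requirement. SAP 6.3.1 treats the OP count as not evaluable below 14 diary days. The stratum falls back on the RTSM value when actual data are missing (SAP 6.2.5.1), but a continuous count would have no such fallback. Such subjects should be few, since eligibility requires 24 completed reports in the first 28 days.

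**Conclusion.** The point holds as an efficiency recommendation. The primary model discards the within-stratum part of the OP count, roughly 27-37% of its variance under the assumed distributions. For within-stratum slopes of -0.3 to -0.5, restoring it cuts the SE by about 1-3% and lifts power from 90.8% to about 91-92%. The ceiling is about 94% at -0.7, the steepest slope considered, and the gain is zero if the slope is zero. The omission itself is plain in all three places. Its size rests on assumptions about slope, OP distribution and the meaning of the 3.6-day SD. The change is worth making because it costs almost nothing; the planned analysis is not wrong without it.

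**What to change.** Before unblinding at the PCD database lock (SAP 2.3):

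- Add prorated OP migraine days per month as a continuous covariate alongside the 4-level stratum in Protocol 9.3.1.1, SAP 6.3.1.3 and the code in SAP 9.3.1.
- Use the matching OP value in the moderate-or-severe and headache-day models.
- Add the OP count to the J2R and tipping-point imputation models. State a rule for DBT efficacy set subjects with fewer than 14 OP diary days, for example imputing the OP value or using the diary days available, so that none are dropped.
- Align the SAP 3.2 wording on the hypothetical strategy, which now refers to treatment group and stratum only.

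The cost is one model term, the missing-OP rule and the text changes, with no new data. Protocol Section 9 requires a protocol amendment if the change is judged a major modification of the primary analysis. If the data are already unblinded, keep the planned model as primary and report the adjusted one as a labelled sensitivity analysis.

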### J2R Imputation Sensitivity Analysis: DBT Efficacy Analysis Set

A sensitivity analysis of the primary endpoint uses the same model as the main analysis, but with jump to reference (J2R) to impute missing data (i.e., change from OP in the number of total migraine days per month) in Months 1 to 3 for the DBT efficacy analysis set. Placebo is considered the “reference”.

The analysis is performed using the following steps:

- 1) Data are imputed under J2R using specific multiple imputation SAS macros for  $n = 30$  data sets.
  - a) Subjects with <14 days of eDiary efficacy data in a specified month in the on-DBT efficacy analysis period have missing data imputed in that month.
  - b) Data imputation is applied to rimegepant and placebo.
  - c) The imputation model uses the following variables: age, sex, race, 4-level randomization stratum, and treatment group. Race may be reduced to fewer levels (e.g., white versus non-white) based on the availability of data.
  - d) The macros are run in the following order: %part1A; %part1B using  $n = 200$  data sets (Ndraws parameter) and  $n = 100$  for Markov chain Monte Carlo (MCMC) chain thinning (thin parameter); %part2A; and %part2B. Note that the Ndraws and thin parameters may be modified as needed (e.g., to decrease Monte Carlo error and autocorrelation).
- 2) Each imputed data set in step 1 is analyzed using the same model from the main analysis (see Section 9.3.1).
- 3) Results from each model analysis in step 2 are combined to produce a pooled difference in LSM change, SE, 95% CI, and p-value using SAS proc mianalyze.

The corresponding table has the same format as the one for the main analysis.

